Specific Aim 1: To determine the extent to which intra-articular (IA) injection of Zilretta in patients with bilateral knee OA improves physical performance (OARSI recommended physical performance measures).

Primary Hypothesis 1: Bilateral knee intra-articular injection of Zilretta results in improved physical performance detectable at: a) 6 weeks, b) 12 weeks (primary), and c) 24 weeks.

Specific Aim 2: To determine the extent to which IA injection of Zilretta in patients with bilateral knee OA improves physical function (KOOS-PF).

Hypothesis 2: Bilateral knee IA injection of Zilretta results in improved patient-reported physical function (KOOS-PS) at: a) 6 weeks, b) 12 weeks, and c) 24 weeks.

Specific Aim 3: To determine the extent to which bilateral knee IA injection of Zilretta in patients with bilateral knee OA improves quality of life (KOOS-QoL).

Hypothesis 3: Intra-articular (IA) bilateral knee injection of Zilretta in patients with bilateral knee osteoarthritis results in improved quality of life (KOOS-QoL) detectable at: a) 6 weeks, b) 12 weeks, and c) 24 weeks.

B. Background and Significance

Osteoarthritis (OA) is the most common disabling disease in older adults, affecting over 27 million Americans, resulting in significantly impaired function and mobility and a societal economic burden. OA is a joint disorder characterized by structural pathology that involves the whole joint, including cartilage lesions, bone remodeling, osteophyte formation, and joint inflammation, among others, leading to symptoms and loss of normal joint function. OA typically becomes symptomatic later in life, usually after age 50, though it may start earlier, such as when a joint injury has occurred or in familial forms. It is the most common form of arthritis worldwide, affecting an estimated 250 million people; about 80% of people over 65 having radiographic evidence of OA.

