This will be an open-label study to determine the functional effects of IA injection of Zilretta into bilateral knees of 70 subjects with KL grade 2-4 symptomatic knee OA. Measurement of OARSI recommended physical performance measures¹⁰, patient-reported physical function, quality of life and pain at baseline, 6, 12 and 24 weeks will allow assessment of short and long-term effects, consistent with OARSI and OMERACT recommendations. Adverse events will be monitored.

Each subject will participate for up to 24 weeks following the intra-articular Zilretta injection. Enrollment is expected to take approximately 6 months. Total study duration is expected to require at least 12 months.

C. Sample size, statistical methods, and power calculation

In this open-label study, all subjects will receive a single IA Zilretta injection into each knee. Outcome measures will be collected at baseline, 6, 12 (primary) and 24 weeks post-treatment. A 24-week follow-up duration was selected to detect meaningful differences from standard of care (IA corticosteroids - TAcS) and long-term effects, while minimizing the variability that may occur further out from treatment. The overall type I error rate will be controlled with an alpha level of 0.0167 to account for three comparisons at the primary time point.

Based on the respective MDC₉₅ calculated from the standard error of the mean change for OARSI recommended physical performance¹, the effect size for this minimal detectable change is 0.392. To detect an effect size at least this large, with an adjusted alpha of 0.0167 and 80% power, a sample size of 60 would be required. To accommodate up to 14% dropout, we plan to recruit 70 subjects.

D. Subject Criteria (See Vulnerable Populations appendix, if applicable):

Enrollment will be comprised of 70 subjects age 30 and over with symptomatic bilateral knee OA. There will be no exclusions based on sex or ethnic group. Potential subjects will be identified through hospital records, referrals from physicians in the surrounding community, mass mailings, and advertisements posted in area clinics and businesses. Any study-related advertisements will be approved by the IRB prior to use. Subjects will be recruited based upon inclusion and exclusion criteria detailed below.

1. Inclusion Criteria

- Men and women age 30 years or older with symptomatic bilateral knee OA.

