Data regarding subject's demographic, knee radiographs, OARSI recommended physical performance measures, and KOOS subscale responses and NRS pain data will be obtained directly from subjects. All data will be coded with no information that could identify a subject. A master list with patient information and assigned study ID's will be stored in a password-protected file available only to the Principal Investigator and the Research Coordinator. Analyses will be performed on coded files. Physical files (e.g. questionnaires) will be stored in locked file cabinets in the office of the Principal Investigator.

E. Quality Assurance / Monitoring

Study staff will have proper qualifications for data entry and will receive training in data entry procedures to ensure data entered is of highest quality. Data will be entered by researchers into two separate databases developed for this study. Each database will contain the same collection points and then be reconciled to clean the data for analysis and outcome reports to the Principal Investigator. Data will be backed-up daily.

V. Data Analysis and Reporting

A. Statistical and Data Analysis:

The primary analysis will regard the change in the 3 OARSI-recommended physical performance measures between baseline and 12 weeks following injections. The three pre/post change scores will be assessed with one-sample t-test for matched pairs, using an alpha level of (.05/3) to determine statistical significant change.

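### The fixed .05/3 rule for the three week-12 tests is valid, but Holm's step-down procedure keeps the same .05 family-wise bound and gives more power when more than one effect is real

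*Combined protocol and SAP*

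**What the plan says.** Section V.A (Statistical and Data Analysis) defines the primary analysis as the baseline-to-week-12 change in three performance measures: "The three pre/post change scores will be assessed with one-sample t-test for matched pairs", "using an alpha level of (.05/3) to determine statistical significant change".

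Section II.C (Sample size, statistical methods, and power calculation) says the overall type I error will be "controlled with an alpha level of 0.0167 to account for three comparisons at the primary time point". It sizes the trial at that same level. One effect size is given ("the effect size for this minimal detectable change is 0.392"), and "with an adjusted alpha of 0.0167 and 80% power, a sample size of 60 would be required". It then adds: "To accommodate up to 14% dropout, we plan to recruit 70 subjects".

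The two sections agree with each other. Neither mentions a step-down procedure. The documents do not state whether the tests are one-sided or two-sided, how strongly the three change scores are correlated, or whether success means any one, a particular one, or all three tests significant.

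**The concern.** A fixed .05/3 holds every test to the strictest cut-off, even after one or two of the others have already been rejected. Holm's procedure orders the three p-values and compares the smallest with .05/3, the next with .05/2 and the largest with .05, stopping at the first failure. It controls the family-wise error at .05 whatever the correlation, and it rejects everything that Bonferroni rejects.

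What is at stake is power on the second and third measures. Section II.C applies one effect size to the whole set, and section V.B expects physical performance to improve. Several real effects is therefore the plan's own scenario, and it is the scenario in which a step-down rule helps most.

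**Working it through.** **Inputs from the documents.** Three paired t-tests (V.A); per-test level .05/3, or 0.0167 (V.A, II.C); standardised effect 0.392, 60 evaluable, 80% power, 14% dropout, 70 recruited (II.C).

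**Assumptions, because the documents are silent.** Sidedness: both computed. Correlation between change scores: equal for all pairs, from 0 to 0.9.

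**Step 1: the plan's own figure.** The normal approximation is n = (z_alpha + z_0.80)² / 0.392², where z_alpha is the critical value. Exact power uses the noncentral t with 59 degrees of freedom and noncentrality 0.392 × √60 = 3.04.

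- One-sided 0.0167: approximation 57.4; exact n = 60, power 80.3%. The stated 60 reproduces.
- Two-sided 0.0167: approximation 68.1; exact n = 71 (72 at exactly .05/3). Power at n = 60 is 71.5%. The stated 60 does not reproduce.
- Dropout: 60 / (1 − 0.14) = 69.8, rounded up to 70. This reproduces.

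**Step 2: Bonferroni against Holm.** Simulation of three paired t-tests, n = 60, all three effects 0.392, 60,000 replicates per setting. Per-test figures are averages over the three tests.

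| Sides | Correlation | Per-test: Bonferroni → Holm | Gain (points) | All three significant: Bonferroni → Holm |
|---|---|---|---|---|
| Two | 0 | 71.6% → 81.2% | 9.6 | 36.7% → 59.7% |
| Two | 0.5 | 71.5% → 79.2% | 7.8 | 48.5% → 66.6% |
| Two | 0.7 | 71.3% → 78.3% | 7.0 | 54.0% → 70.3% |
| Two | 0.9 | 71.7% → 77.1% | 5.4 | 62.2% → 74.3% |
| One | 0 | 80.4% → 89.3% | 8.9 | 52.0% → 74.9% |
| One | 0.5 | 80.2% → 87.3% | 7.2 | 61.2% → 78.6% |
| One | 0.7 | 80.3% → 86.7% | 6.4 | 66.2% → 81.2% |
| One | 0.9 | 80.1% → 85.1% | 5.0 | 72.0% → 83.2% |

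The gain in the chance that all three are significant runs from 83.2 − 72.0 = 11.2 points to 59.7 − 36.7 = 23.0 points. The chance of at least one significant test is identical under the two rules (two-sided, correlation 0.5: 91.0% for both), because the first Holm step is the Bonferroni test.

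**Step 3: when the gain shrinks.**

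- Only two effects real: 2.6 to 3.9 points on each of those two (correlations 0 to 0.8).
- Only one effect real: 0 to 0.2 points.
- All 70 evaluable, all three effects 0.392: 3.9 to 8.4 points.
- All three effects 0.5 (n = 60, correlation 0.5): about 2.7 points one-sided and 3.9 two-sided.

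**Step 4: error control.** With no real effect, simulated family-wise error was 3.4% to 5.0%, the same for both rules. With one or two real effects Holm stayed at or below 5% within simulation error, but it used more of the allowance. For example, with two real effects, two-sided, correlation 0.5, the error on the null measure rose from 1.6% to 3.6%.

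**The case against.** The strongest reply is that there is nothing to correct. The rule is pre-specified, the same in both sections, valid for three comparisons, and the level at which the trial was sized. Plain Bonferroni is a legitimate conservative choice in an open-label pilot. All of that stands, and it is why this is offered only as an improvement.

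A second reply is that the benefit depends on a success rule the documents never state. If success means any one significant measure, Holm adds nothing. That also stands. However, V.A assesses each of the three change scores for significance, so the number of measures shown to improve will be reported.

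Third, Holm has a reporting price. Any test rejected by Holm but not by Bonferroni has p above .05/3, so with two-sided tests its 98.3% interval must include zero. Aim 1 asks about the extent of improvement, so a significant result beside such an interval needs explaining. Holm is therefore not free.

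A reader might also infer that the plan falls short of 80% power and that Holm restores it. The documents do not support this. The shortfall (80 − 71.5 = 8.5 points) exists only if testing is two-sided, which is not stated. Primary Hypothesis 1 is directional, and the stated 60 reproduces one-sided. Even under two-sided testing, Holm gives back 2.9 to 3.9 of the 8.5 points if two effects are real, and essentially none if one is.

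**Conclusion.** The point holds as a cheap gain in efficiency. Holm's validity and its dominance over the fixed rule are general facts that need no assumption about this trial. Only the size of the gain does. With 60 evaluable subjects and all three effects at 0.392, average per-test power rises by about 5 to 10 points and the chance that all three are significant by about 11 to 23 points, for assumed correlations from 0.9 down to 0 and either sidedness. With two real effects the per-test gain is about 2.5 to 4 points, with one about none, and for at least one rejection none.

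A flat claim of 7 to 10 points per test would go too far. It needs two-sided tests, 60 evaluable subjects, three real effects near the planned size and a correlation no higher than about 0.7, and the documents establish neither the sidedness nor the correlation. Nor is the error rate itself the same under both rules: the .05 bound is shared, but Holm uses more of it when some measures do not change.

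**What to change.** In section V.A, with a matching edit in II.C, replace the fixed .05/3 rule with: *The three p-values will be tested by Holm's step-down procedure at a family-wise level of .05.* Use the same sidedness as the sample-size calculation. That sidedness is unstated; this is a separate issue, to be settled on its own.

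Make the change before any 12-week data are seen. The study is open-label and V.A plans a soft-lock after week 12, so a later change would look data-driven.

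Keep 98.3% confidence intervals for the three mean changes as a conservative display. State in the report that, with two-sided tests, a measure significant only through Holm will have a 98.3% interval that includes zero.

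The cost is one sentence, the matching edit and that reporting note. No subjects, visits or measurements are added. II.C should still describe its power figure as calculated at 0.0167 per test, because Holm does not alter or repair that calculation.

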University of Kansas Medical Center
RESEARCH PROTOCOL INVOLVING HUMAN SUBJECTS TEMPLATE

Version date: October 1, 2018

Principal Investigator: [name], MS

Study Title: An open-label pilot study of the effect of intra-articular bilateral knee injections of Zilretta on OARSI recommended physical performance measures in adults with symptomatic knee osteoarthritis.

Co-Investigator(s): [name]

I. Purpose, Background, and Rationale

A. Aim and Hypotheses

This study will be an open-label trial to determine the functional effects of bilateral IA injections of Zilretta into knee joints of 70 subjects with bilateral KL grade 2-4 symptomatic knee osteoarthritis (OA). Measurement and evaluation of outcomes at baseline, 6, 12 and 24 weeks will allow assessment of short and long-term effects, consistent with Osteoarthritis Research Society International (OARSI) and Outcome Measures in Rheumatology (OMERACT) recommendations.

The **primary** aim of the proposed study is to demonstrate the effect of IA injection of Zilretta on physical performance measures in adults with bilateral knee OA. We will test this primary study endpoint by assessing the change in OARSI recommended physical performance tests¹ (30-second chair standing test, 40m fast-paced walking test, stair ascent) 6, 12 (primary) and 24 weeks after treatment.

The secondary outcome will be the change in Knee Injury and Osteoarthritis Outcome Score (KOOS-PS) at 6, 12 (main) and 24 weeks after treatment. This will be captured using the patient-reported physical function short form.

The tertiary outcomes will be the change in KOOS-Quality of life subscale (QoL) and Numerical Rating Scale (NRS) for pain. While the primary outcomes will be defined at the 12-week follow-up, all outcomes will be assessed at the 6- and 24-week follow-up as well to define the course and trajectory of effects.

We hypothesize that people with bilateral symptomatic knee OA will experience significant improvement in physical performance, physical function and quality of life for at least 12 weeks following treatment. Based on research done using Zilretta in patients with knee OA, we anticipate that it will have a greater magnitude and duration of analgesic effect along with significantly fewer adverse events when compared to the rates reported for standard of care therapy (i.e. immediate release corticosteroid injection).²

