Differences between baseline and other timepoints and secondary/tertiary outcome measures will be assessed with repeated measures analyses, with time as a repeated factor to account for multiple comparisons over time. A soft-lock of the database will occur after the 6- and 12-week time points. The analyses of secondary and tertiary outcomes will involve the analyses of longitudinal data, collected at baseline, 6 weeks, 12 weeks, and 24 weeks. These response variables will be modeled using the framework of longitudinal mixed models. Each model will be based on two main effects: a random subject effect, and a fixed time effect consisting of four levels (baseline, 3 follow-up time points). The distribution of the secondary and tertiary outcome measures will be examined and transformation to a normal distribution will be performed if needed. We will use the Akaike information criterion to determine an appropriate variance/covariance structure. Each of the hypotheses of interest will be tested by examining appropriate contrasts and estimable linear forms in the overall mean and the main effects for time. Analyses will be conducted using SAS (Version 9.1.2). PROC MIXED will be used to fit the longitudinal models.

B. Outcome: We expect statistically significant and clinically meaningful improvement in physical performance, physical function, pain and quality of life 12 weeks following bilateral treatment with Zilretta.

C. Study results to subjects: The study will be registered on www.clinicaltrials.gov and results posted upon completion of the study.

D. Publication Plan: Results will be submitted for presentation at an appropriate conference and for publication in an appropriate journal for the topic of study.

VI. Bibliography / References / Literature Cited

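### Section V.A credits the repeated time factor with handling multiple comparisons over time; it does not, and no procedure is stated for the non-primary visit contrasts

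*Combined protocol and SAP*

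**What the plan says.** Type I error control is stated for one family only. Section II.C sets "an alpha level of 0.0167 to account for three comparisons at the primary time point", and V.A repeats it for the three baseline-to-week-12 performance changes, "using an alpha level of (.05/3) to determine statistical significant change".

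For the other visits and for KOOS-PS, KOOS-QoL and NRS pain, V.A uses a mixed model with a random subject effect and a four-level fixed time effect, "with time as a repeated factor to account for multiple comparisons over time". It then says that the "hypotheses of interest will be tested by examining appropriate contrasts and estimable linear forms in the overall mean and the main effects for time". It names no level, multiplicity adjustment, testing order or gate for those contrasts.

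The plan does rank visits. Section I.A makes the secondary outcome the "change in Knee Injury and Osteoarthritis Outcome Score (KOOS-PS) at 6, 12 (main) and 24 weeks after treatment", and V.B expects "improvement in physical performance, physical function, pain and quality of life 12 weeks following bilateral treatment with Zilretta". Section I.A also says that "all outcomes will be assessed at the 6- and 24-week follow-up as well to define the course and trajectory of effects". V.A does not turn any of this into a sequence of tests.

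**The concern.** The sentence in V.A states a purpose that the method does not serve. Fitting time as a repeated factor gives each visit contrast a standard error that respects the correlation within a subject. Each contrast then rejects at its own nominal rate, and the chance of at least one false rejection still grows with the number of visits tested.

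The contrasts are presented as tests. The specific aims list each hypothesis separately at 6, 12 and 24 weeks, and V.A says the hypotheses will be tested. A report that follows V.A could describe a significant 6- or 24-week result as already protected against having looked at several visits, when nothing in the plan protects it. The 24-week result bears on how long any benefit lasts, so the wording matters there.

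**Working it through.** **1. The plan's own figures.**
- Primary level: 0.05/3 = 0.0167, as stated.
- Sample size: paired t-test, noncentral t, d = 0.392 (II.C: "the effect size for this minimal detectable change is 0.392"), alpha 0.0167, n = 60. One-sided power is 0.803, so N = 60 reproduces. Two-sided power is 0.715, and 71 subjects would be needed. The plan does not state sidedness, so both bases are shown below.
- Dropout: 60/(1 − 0.14) = 69.8, so 70 reproduces.

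**2. Number of contrasts within one outcome.**
- Each performance test: two non-primary visits (6 and 24 weeks).
- KOOS-PS: two if the main 12-week visit is kept apart, three if the visits are read equally.
- KOOS-QoL and NRS: three.

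**3. Correlation between contrasts.** Under compound symmetry with variance σ² and correlation ρ, Var(Y_j − Y_0) = 2σ²(1 − ρ) and Cov(Y_j − Y_0, Y_k − Y_0) = σ²(1 − ρ). The contrasts therefore correlate at 0.5 whatever ρ is. V.A leaves the covariance structure to the Akaike criterion, so I assume r = 0.3 to 0.7.

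**4. Error when no visit has an effect.** Assume 0.05 per contrast, because the plan gives no level. For k contrasts with common correlation r and critical value c (1.960 two-sided, 1.645 one-sided):

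error = 1 − ∫ φ(z) {Φ[(c − z√r)/√(1 − r)] − Φ[(−c − z√r)/√(1 − r)]}^k dz

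The second Φ term is omitted for one-sided tests.

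| Visits, basis | r = 0.3 | r = 0.5 | r = 0.7 |
|---|---|---|---|
| 2, two-sided | 0.0951 | 0.0907 | 0.0835 |
| 3, two-sided | 0.1362 | 0.1254 | 0.1092 |
| 2, one-sided | 0.0929 | 0.0878 | 0.0804 |
| 3, one-sided | 0.1303 | 0.1184 | 0.1027 |

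A simulation of the V.A model (n = 60, four visits, compound symmetry, no effect, two-sided 0.05) agrees. Each contrast rejects about 5% of the time and at least one of three about 12 to 13% of the time, with time in the model as a repeated factor throughout.

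**5. If 0.0167 per contrast had been meant.** The two-sided error would be 2.9–3.3% (two visits) or 3.9–4.8% (three). II.C and V.A tie that level to the primary time point only.

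**6. If an overall time test were used as a gate.** In the same simulation, requiring a significant F-test at 0.05 first gives about 4% when no visit has an effect. When one visit has a real effect (1 SD), the gate opens and the error across the other two visits is about 9%.

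**The case against.** The best defence is that V.A implies an overall test. It names a four-level time effect and refers to main effects for time, so an F-test followed by contrasts is a natural reading, and that holds the error near 4% when nothing changes at any visit. This softens the criticism but does not remove it. V.A does not make the overall test a condition for reading the contrasts, and such a gate stops protecting the remaining visits once one visit has a real effect, which is what V.B expects at 12 weeks.

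The second defence is proportion, and it stands. This is a single-arm, open-label pilot, and the 6- and 24-week data are there to describe a trajectory. Change from baseline can also arise without any drug effect, which no adjustment over visits addresses. How results will be worded in a report is conjecture.

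A reader might infer more than the documents support:
- **That the primary result is exposed.** It is not; the three 12-week tests have their own stated level.
- **That the plan tests these contrasts unadjusted at 0.05.** It does not say so; it is silent.
- **That error should be counted over all outcomes together.** The sentence makes a claim about time only, so the point stays within one outcome.
- **That left- and right-knee pain double the NRS contrasts.** Pain is rated in each knee, but the documents do not say that two values are analysed, and two knees would be two variables rather than more visits of one.

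**Conclusion.** The point holds, as a minor one. V.A claims a property that its method lacks, and nothing else in the plan supplies it for the non-primary visit contrasts. At an assumed 0.05 per contrast and correlation 0.3 to 0.7, the error within one outcome when no visit has an effect is 8.4–9.5% (two visits) or 10.9–13.6% (three) two-sided, and 8.0–9.3% or 10.3–13.0% one-sided. These sizes depend on the assumed level and correlation. The conclusion that a repeated factor does not adjust for several visits depends on neither. The primary analysis and the sample size are untouched.

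**What to change.** **Default.** In V.A, end the sentence after naming time as a repeated factor and delete the clause about multiple comparisons. Label all non-primary contrasts supportive or exploratory, with nominal p-values and confidence intervals and no claim that multiplicity over time was handled. This is a wording change that costs no subjects and no power. The downside is that 6- and 24-week results cannot be worded as confirmed.

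**If the sponsor wants control instead,** name one procedure in advance and state its level and sidedness.

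- *KOOS-PS, KOOS-QoL, NRS:* either test 12 weeks first at 0.05 and, only if significant, 6 and 24 weeks at 0.025 each; or use a Dunnett adjustment of the three visits against baseline (two-sided nominal threshold about 0.0188 at r = 0.5). The documents give no effect size for these outcomes. At assumed d = 0.3, 0.392 and 0.5 (n = 60, two-sided), the first option keeps 12-week power at 63%, 85% and 97%. It leaves about 40%, 69% and 92% at each of 6 and 24 weeks (equal effects, r = 0.5), and neither can be claimed if 12 weeks fails. Dunnett gives 47%, 73% and 92% at every visit.
- *Performance tests:* 6 and 24 weeks at 0.025 each, stated as a family separate from the 12-week primary. That pair has an error of 4.3–4.8% (two-sided). It must not be described as 5% per outcome: applying the formula above with levels 0.0167, 0.025 and 0.025 gives 0.063, 0.059 and 0.052 at r = 0.3, 0.5 and 0.7, so 5.2–6.3% once the primary is counted. Per-visit power at d = 0.392, n = 60 falls from about 85% to 77% (two-sided) or from about 91% to 85% (one-sided).

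Under either route, state that there is no adjustment across outcomes.
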